5.8.4. Vital Sigs

Descriptive summary statistics of the observed values for blood pressure (systolic and diastolic), heart rate, temperature and respiratory rate data collected at screening, baseline and post-baseline visits will be presented by treatment group. As temperature is collected twice daily while a participant is hospitalized, the average of the daily measurements will be used. Boxplots will be

used to display the distribution of the observed values over time, using all post baseline assessments, by treatment group.

Participants with clinically significant values for any vital signs are to be reported as an AE and therefore clinically significant vital sign findings will be interpreted from the AE summaries.

5.8.5. 12-Lead ECG

Descriptive summary statistics of the observed values for 12-lead ECG data at screening, baseline and each post-baseline visit (i.e., Day 5/Discharge, Day 10/Discharge, 14, 21 and 28) will be presented by treatment group. Boxplots will be used to display the distribution of the observed values over time, by treatment group.

Participants with clinically significant values for any 12-lead ECG findings are to be reported as an AE and therefore clinically significant 12-lead ECG findings will be interpreted from the AE summaries.

5.8.6. Physical Exam

A complete physical exam is planned for screening and day 10. A limited physical exam is planned for baseline, day 5, 14, 21 and 28.

At each time point, findings that are both abnormal and clinically significant will be summarized using frequency counts and percentages, with the number of participants in the safety set used as the denominator.

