1.2. Schedule of Activities (SoA)

Table 2: Schedule of Activities

General Notes:

- In case of natural disasters or pandemics, some visits/study procedures can be done via virtual visits (e.g., telemedicine or telephone) or at home visits after hospital discharge. Refer to study reference manual for more details.
- Assessments completed as part of standard of care within the protocol defined windows, will not need to be repeated specifically for the protocol.

Procedure	Screening	Treatment Period			Follow-up			Post-study visit	Notes
		BL	Daily visits [‡]	EOT/ET*			EOS		
Study Day	-3 to -1	1	2-9	10	14	21	28	+60 days from EOS	Baseline (BL); End of Treatment (EOT), Early termination (ET); End of study (EOS) [‡] If a subject is discharged prior to Day 10, they will complete Day 5 and Day 10 visits assessments * This visit will be conducted at hospital discharge, if subject is discharged prior to Day 10
Visit window (days)				±1	±2	±2	±2	±10	
Informed consent	X								
Inclusion and exclusion criteria	X	X							
Demography	X								
Medical history	X								
Current medical conditions	X	X							Including time from onset of symptoms (fever, cough, etc.) to study entry, COVID-19 severity for each subject
Comprehensive physical exam	X			X					
Height and weight	X			X*					*Weight only

Procedure	Screening	Treatment Period			Follow-up			Post-study visit	Notes
		BL	Daily visits [‡]	EOT/ET*			EOS		
Study Day	-3 to -1	1	2-9	10	14	21	28	+60 days from EOS	Baseline (BL); End of Treatment (EOT), Early termination (ET); End of study (EOS) ‡ If a subject is discharged prior to Day 10, they will complete Day 5 and Day 10 visits assessments * This visit will be conducted at hospital discharge, if subject is discharged prior to Day 10
Visit window (days)				±1	±2	±2	±2	±10	
Limited physical exam		X	Day 5		X	X	X		Physical exam will be symptom-directed exam
Hematology	X	X	Day 5	X	X	X	X		Refer to Section 10.2
Clinical chemistries	X	X	Day 5	X	X	X	X		Refer to Section 10.2
INR	X						X		International normal ratio (INR)
Urinalysis	X						X		Refer to Section 10.2
Sputum samples and nasopharyngeal swab for SARS-CoV-2 PCR		X	Day 5	X	X	X	X		Samples to be frozen as specified in the laboratory manual for viral quantification.
Serum hsCRP and ferritin		X	Day 5	X	X	X	X		High sensitivity c-reactive protein (CRP)
Reserve blood sample for biomarker analyses		X	Day 5	X	X	X	X		Date and times to be recorded when samples were collected.
IL-6		X	X	X	X	X	X		Interleukin 6 (IL-6)

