9.4.1. General

In general, summary tabulations will be presented that display the number of observations, mean, standard deviation, median, minimum, and maximum for continuous variables, and the number and percent (of non-missing values) per category for categorical data.

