3.0	22 October 2020	
Added additional details on how to derive FiO2 values based on oxygen flow rates.
 
Changed IL-6 sub-group analysis from > ULN to > median,
	
eCRFs collected flow rate or FiO2. Additional details on how to derive FiO2 were needed for programming.
 
IL-6 values do not have normal ranges

1. Introduction

This Statistical Analysis Plan (SAP) contains a more technical and detailed elaboration of the principal features of the analysis described in the protocol and includes detailed procedures for executing the statistical analysis. This SAP should be used in conjunction with the protocol. If there are any discrepancies between the protocol and SAP, this SAP will prevail. Any deviations from this SAP that are implemented in the final analysis will be documented with sound clinical and statistical rationale in the Clinical Study Report (CSR). In the event of any changes to the primary endpoints or analyses, these changes will be documented through a protocol amendment, consistent with ICH E9.

A separate document contains the table, figure and listing specifications and any example programming codes.

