where $z_{\alpha/2}$ and z_{β} are the value from a standard normal distribution, π is the proportion of participants randomized to control, $1 - \pi$ is the proportion of participants randomized to active and θ is the standardized effect size we wish to detect. For this study $\alpha = 5\%$, $\beta=10\%$, $\pi=1/3$ and $\theta=0.625$ (i.e., $25/40$).

4. Analysis Sets

For purposes of analysis, the following populations are defined:

Population	Description
Enrolled	All randomized participants
Full Analysis Set (FAS)	All randomized participants who receive at least one dose of study drug. This population will be used for all efficacy analyses
Modified Intent to Treat (MITT)	All randomized participants who receive at least one dose of study drug and one post baseline assessment of the SpO ₂ /FiO ₂ ratio. This population will be used for the primary and secondary endpoints related to improvement in SpO ₂ /FiO ₂ ratio.
Per Protocol Analysis Set (PP)	All randomized participants who receive at least 6 doses of study drug without any major protocol violations that would impact the assessment of the primary efficacy endpoints. This population will be used for efficacy analyses of the primary efficacy endpoints
Safety Analysis Set	All enrolled participants who receive any study drug
PK Analysis Set	All enrolled participants who receive any study drug and have plasma concentration data

5. Statistical Analyses

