5.1. General Considerations

The following is a list of general reporting conventions:

- Percentages will be based on the number of participants in the analysis set unless otherwise indicated.
- Categorical variables will be summarized using counts (n) and percentages (%) and will be presented in the form of n (%).
- Percentages will be reported to 1 decimal place.
- Continuous data will be summarized using the mean, standard deviation (SD), median, minimum, 25th and 75th percentiles, maximum, and number of participants with data.
- Means and medians will be reported at 1 more significant digit than the precision of the data. Standard deviations and confidence intervals will be reported at 2 more significant digits than the precision of the data. Quartiles, minima and maxima will be reported to the same level of precision as the original observations.
- The median will be reported as the average of the 2 middle numbers if the dataset contains even numbers.
- No preliminary rounding should be performed; rounding should only occur after analysis. To round, consider digit to right of last significant digit: if < 5 , then round down; if ≥ 5 , then round up.
- All p-values will be 1-sided and reported to 3 decimal places (e.g., 0.XXX). Values < 0.001 will be reported as < 0.001 .

If departures from these general conventions are present in the specific evaluations sections of this SAP, then those conventions will take precedence over these general conventions.

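### Per-visit physical-examination percentages use the whole safety set as denominator, so participants not examined at a visit are in effect counted as having no finding

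*SAP*

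**What the plan says.** SAP 5.8.6 plans a complete examination at screening and Day 10, and adds: "A limited physical exam is planned for baseline, day 5, 14, 21 and 28". The summary is by visit: "At each time point, findings that are both abnormal and clinically significant will be summarized". The results are to be "summarized using frequency counts and percentages, with the number of participants in the safety set used as the denominator". SAP section 4 defines the safety set as "All enrolled participants who receive any study drug", with no requirement of an examination at any visit.

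The general rule in SAP 5.1 points the same way: "Percentages will be based on the number of participants in the analysis set unless otherwise indicated". SAP 5.8 leaves missing safety data missing unless otherwise specified. Nothing in the SAP limits the physical-examination denominator to those examined.

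Protocol 9.4.1 takes the other route. Its general tabulations show "the number and percent (of non-missing values) per category for categorical data". On conflicts, the SAP introduction states: "If there are any discrepancies between the protocol and SAP, this SAP will prevail". The SAP gives no reason for changing the denominator, in its version history or elsewhere.

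The general notes to the Schedule of Activities (Protocol 1.2) say that in a pandemic "some visits/study procedures can be done via virtual visits (e.g., telemedicine or telephone) or at home visits after hospital discharge".

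**The concern.** A visit-specific finding can be recorded only in someone who is alive, in the study and physically examined at that visit. Dividing by everyone ever dosed puts the rest in the table as if they had been examined and found normal. That sits badly with the SAP's own rule of leaving missing safety data missing.

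Two misreadings follow. A percentage that declines over follow-up can look like resolution when only the number examined has declined. And if the arms differ in death, withdrawal or remote-visit rates, the arm with fewer examinations looks cleaner.

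The reader may be unable to undo this. SAP 5.1 requires the number of participants with data for continuous summaries but not for categorical ones, so the table need not show how many were examined.

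Other tables may not carry the same information. For laboratory values, vital signs and ECG, SAP 5.8.3 to 5.8.5 state that clinically significant values are reported as AEs and read from the AE summaries. SAP 5.8.6 has no such sentence. Protocol 10.3.1 also excludes from the AE definition abnormal safety assessments associated with the underlying disease, unless they are more severe than expected. Some clinically significant findings, for example respiratory ones, may therefore appear only in this table.

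**Working it through.** The plan states no expected rate of abnormal examinations and no per-visit missing rate, so there is no figure of its own to reproduce. The check is an identity plus illustrations.

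**Notation.** N = safety-set participants in an arm (SAP section 4; planned 80 active and 40 control). E = those examined at the visit. x = those with a clinically significant abnormal finding, all of whom are among the E. m = 1 − E/N, the unexamined share.

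**Identity.** Reported percentage = x/N = (x/E) × (E/N) = (percentage among those examined) × (1 − m). Relative to the percentage among those examined, the reported figure is lower by exactly m. The two agree only when m = 0.

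**Illustration.** Assume 20% abnormal among those examined. The values of m are also assumptions. The first three are close to the hospital fatality estimate and interval in Protocol 2.2 (14%, 6.2% to 21.5%), used here only to set a range.

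| Unexamined share m | Reported percentage |
|---|---|
| 0% | 20 × 1.00 = 20.0% |
| 6% | 20 × 0.94 = 18.8% |
| 14% | 20 × 0.86 = 17.2% |
| 22% | 20 × 0.78 = 15.6% |
| 30% | 20 × 0.70 = 14.0% |

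In whole participants, with m near 30% in the active arm, 56 of 80 are examined. Eleven findings give 11/56 = 19.6% of those examined but 11/80 = 13.8% as planned. With m near 14% in the control arm, 34 of 40 are examined. Seven findings give 7/34 = 20.6% against 7/40 = 17.5%.

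**Between arms.** With 20% among those examined in both arms, and 90% examined in one against 70% in the other (assumed), the table shows 20 × 0.90 = 18% against 20 × 0.70 = 14%. The whole difference comes from the examination rates.

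**Which visits.** Screening and baseline should be almost unaffected. A note in the Schedule of Activities has participants discharged before Day 10 still complete the Day 5 and Day 10 assessments, so losses there come mainly from death and withdrawal. By Days 14, 21 and 28, deaths and withdrawals have accumulated and remote post-discharge visits are allowed, so these visits are the most exposed.

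**The case against.** The strongest objection is that the percentage among those examined is not the true rate in the arm either. Remote visits happen after discharge, so unexamined survivors are plausibly the recovered ones. Suppose, purely for illustration, that 80 are alive: 40 in hospital with 30% abnormal (12), and 40 at home, unexamined, with 5% abnormal (2). The rate in all 80 is 14/80 = 17.5%. The planned denominator gives 12/80 = 15%, and the number examined gives 12/40 = 30%. For participants who have died, a visit-specific rate is not defined at all. This stands. The percentage of treated participants with an observed finding is also a legitimate descriptive quantity. A changed denominator therefore needs a clear label and the counts of those not examined.

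Several stronger readings are tempting but unsupported:

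- **A fixed size.** A reader might apply the 14% fatality figure and infer an understatement of at least 14%. Adding 20% remote visits among survivors would give 0.86 × 0.80 = 0.688, or about 31%. But 14% is a literature figure for hospitalized patients in general. Protocol 5.1.2 excludes those requiring at least 0.75 FiO₂ and those requiring or expected to require mechanical ventilation. The remote-visit share is in neither document.
- **Every remote visit loses an examination.** A home visit may allow one. Which procedures may be remote is left to a study reference manual outside these documents.
- **All per-visit categorical tables are affected.** The 6-point ordinal scale (Protocol 8.1.3, SAP 5.6.2) has categories for death and for not being hospitalized, so these are scored outcomes there. Vital signs and ECG are planned as descriptive statistics and boxplots of observed values.
- **The protocol is breached.** Protocol 9.4.1 is worded as a general rule, Protocol 9.4 lets the SAP modify plans, Protocol 9.4.3 plans no physical-examination summary, and the SAP prevails. What remains is an unexplained departure.

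Findings not attributed to the underlying disease should also reach the TEAE tables through Protocol 10.3.1. That limits the consequence without removing the defect in this table.

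**Conclusion.** The point holds as a defect of presentation in one table. SAP 5.8.6 combines a numerator that requires examination with a denominator that does not, so the reported percentage mixes the frequency of findings with the frequency of examination. That is exact and needs no assumption. Calling it an understatement of the rate in the whole arm would require unexamined participants to resemble those examined, and the documents do not support that.

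The size cannot be determined from the documents; the figures above show the range under assumed missing shares. The effect should be smallest early and largest from Day 14 on. Physical examination is not an endpoint, all safety analyses are descriptive, counts accompany the percentages, and no hypothesis test is touched. It is worth correcting because it costs little and the table may be the only place where some disease-related findings appear.

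**What to change.** In SAP 5.8.6, set the denominator to the number of safety-set participants with a physical examination at that time point, and label the column as *percent of those examined*. Print by arm and time point the number examined and the number not examined, split into died, withdrawn, and remote or missed visit. The split matters because those still examined late may be sicker than those who were not.

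SAP 5.1 can stay as it is, since it yields to specific sections. Keep the full safety set as denominator for cumulative TEAE incidence in SAP 5.8.2, and leave the 6-point ordinal scale unchanged. State in 5.8.6 that the choice follows Protocol 9.4.1.

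The cost is a sentence or two and a change to one table program; no new assessments are needed. The downside is that denominators vary by visit and the percentages become somewhat higher.

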5.9. Other Analyses

5.9.1. Pharmacokinetic Analyses

BLD-2660 plasma concentrations collected on Day 5 pre-dose and 1-2 hours post dose will be summarized using descriptive statistics, by time point.

Pharmacokinetic parameters may be estimated using a population PK approach. Details of this analysis will be provided in a separate analysis plan.

5.9.2. Pharmacodynamic Analyses

The following pharmacodynamic parameters will be summarized using descriptive statistics, by time point and treatment group:

- IL-6
- D-Dimer

Both the observed value and the change from baseline value will be summarized. Participants who are discharged prior to day 10, will have their end of treatment assessment, mapped to day 10.

To compare the change in these parameters over time a MMRM model will be used. Missing data will be assumed to be missing at random and maintained as missing. The Kenward-Roger method will be used to calculate the denominator degrees of freedom for the test of fixed effects and adjusted standard errors. The model will include baseline value as a covariate, treatment, visit and visit-by-treatment interaction terms as categorical fixed effects, and participant as a random effect. An unstructured covariance matrix will be assumed to model the within-participant errors. This variance-covariance matrix will be estimated across treatment groups. However, if there is a convergence problem with the unstructured covariance matrix, then alternative covariance structures will be examined (heterogeneous Toeplitz structure, Compound Symmetry) and the one with the best fit as determined by the Akaike information criteria (AIC) (i.e., smallest AIC value) will be used. The least squares means (LS-means) for each treatment, LS-means treatment difference and corresponding confidence interval (CI) for the LS-means difference and p-value for the treatment difference, will be reported at each visit. For each parameter, a plot of the LS-means (and 95% CI), over time and by treatment group, will be produced.

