6.4. Measures to Minimize Bias: Randomization and Blinding

All subjects will be centrally assigned to randomized study drug using an Interactive Response Technology (IRT). Before the study is initiated, the log in information & directions for the IRT will be provided to each site.

Randomization will be stratified by remdesivir use at study entry (yes/no)

Study drug will be dispensed by the unblinded pharmacy staff to the study staff/research nurse in a blinded manner per the schedule summarized in the SoA ([Section 1.2](#)).

The IRT will be programmed with blind-breaking instructions. Subject safety must always be the first consideration in making such a determination. If the Investigator decides that unblinding is warranted, the Investigator should make every effort to contact the Sponsor prior to unblinding a subject's drug assignment unless this could delay emergency treatment of the subject. If a subject's drug assignment is unblinded, the Sponsor must be notified within 24 hours after breaking the blind. The date and reason that the blind was broken must be recorded in the source documentation and case report form, as applicable.

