9.4.4. Other Analyses

BLD-2660 plasma concentrations will be summarized using descriptive statistics. Pharmacokinetic parameters will be estimated using a population PK approach.

Change from baseline in IL6 and D-dimer will be analyzed using a repeated measure mixed effects model. Missing data will be assumed to be missing at random. The model will include fixed effects for treatment group, and remdesivir use (yes vs no). Additional covariates may be included if warranted. Subjects will be treated as random, with an unstructured covariance structure. The least square (LS) means, and 95% confidence intervals within treatment and for the treatment difference will be reported at each timepoint.

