1.1. Objectives and Endpoints

Objectives	Endpoints
Primary	

 To evaluate clinical benefit of BLD-2660 in hospitalized adults with recently diagnosed SARS-CoV-2 infection 	
 Time to recovery as defined by no longer requiring oxygen support or hospital discharge, whichever occurs first

 To evaluate improvement in oxygenation in hospitalized adults with COVID-19 treated with BLD-2660 	
 Change from baseline to Day 10 or hospital discharge, if sooner, in the ratio of peripheral hemoglobin oxygen saturation to fraction of inspired oxygen (SpO₂/FiO₂)
Secondary	

 To evaluate the safety and tolerability of BLD-2660 in the same population 	
 Incidence of TEAEs and serious adverse events (SAEs)

 To evaluate improvement in Biomarkers 	
 Change from baseline to Days 10/EOT, 14, 21 and 28 in serum calprotectin

 Additional efficacy outcomes 	
 Time to hospital discharge readiness Proportion of participants reporting each 6-point ordinal scale of the clinical status outcome assessment Change from baseline to Days 10/EOT, 14, 21 and 28 in IL-6 and D-dimer

Objectives	Endpoints
Exploratory	

 Other efficacy outcomes 	
 Proportion of participants who require mechanical ventilation after study entry

 To evaluate antiviral activity of BLD-2660 in the same population 	
 Change from baseline in SARS-CoV-2 viral load at Days 5, 10/EOT, 14, and 28

 Other safety outcomes 	
 Clinically relevant changes from baseline in electrocardiogram (ECG), and clinical laboratory values at each post baseline time point Proportion of participants with clinically significant drug-related troponin elevations that have repeat elevation upon confirmatory testing as adjudicated by the DMC while continuing study drug during the 10-day treatment period

 To assess population pharmacokinetics (PK) characteristics of BLD-2660 	
 BLD-2660 plasma concentrations

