5.6. Secondary Endpoint(s) Analysis

5.6.1. Key/Confirmatory Secondary Endpoint(s)

Change from baseline in serum calprotectin

Both the observed value and the change from baseline value will be summarized. Participants who are discharged prior to day 10, will have their end of treatment assessment, mapped to day 10.

To compare the change from baseline over time a MMRM model will be used. Missing data will be assumed to be missing at random and maintained as missing. The Kenward-Roger method will be used to calculate the denominator degrees of freedom for the test of fixed effects and adjusted standard errors. The model will include baseline value as a covariate, treatment, visit and visit-by-treatment interaction terms as categorical fixed effects, and participant as a random effect. An unstructured covariance matrix will be assumed to model the within-participant errors. This variance-covariance matrix will be estimated across treatment groups. However, if there is a convergence problem with the unstructured covariance matrix, then alternative covariance structures will be examined (heterogeneous Toeplitz structure, Compound Symmetry) and the one with the best fit as determined by the Akaike information criteria (AIC) (i.e., smallest AIC value) will be used. The least squares means (LS-means) for each treatment, LS-means treatment difference and corresponding confidence interval (CI) for the LS-means difference and p-value for the treatment difference, will be reported at each visit. For each parameter, a plot of the LS-means (and 95% CI), over time and by treatment group, will be produced.

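### The SAP's IL-6, D-dimer and calprotectin models omit the remdesivir stratum, carry a redundant participant random effect and state no rule on transformation

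*SAP*

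**What the plan says.** Randomization (protocol 6.4): "Randomization will be stratified by remdesivir use at study entry (yes/no").

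Protocol 9.4.4, for change in IL-6 and D-dimer: "The model will include fixed effects for treatment group, and remdesivir use (yes vs no"). The same paragraph adds: "Subjects will be treated as random, with an unstructured covariance structure". Calprotectin is not mentioned there or anywhere else in the protocol.

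SAP 1.1 lists two secondary biomarker endpoints: "Change from baseline to Days 10/EOT, 14, 21 and 28 in IL-6 and D-dimer" and "Change from baseline to Days 10/EOT, 14, 21 and 28 in serum calprotectin".

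SAP 5.9.2, for IL-6 and D-dimer, has baseline as a covariate, then treatment, "visit and visit-by-treatment interaction terms as categorical fixed effects, and participant as a random effect". On the covariance it says: "An unstructured covariance matrix will be assumed to model the within-participant errors". If that fails to converge, heterogeneous Toeplitz and compound symmetry are tried and the smaller AIC decides. SAP 5.6.1 gives calprotectin the same model, again with baseline, treatment, visit and their interaction, "and participant as a random effect". Remdesivir appears in neither section, and neither mentions a transformation or a check of normality.

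Elsewhere, SAP 5.5.2 keeps the remdesivir strata in the primary Cox model and the primary MMRM. SAP 5.7 allows a log transform of viral load if normality is violated. SAP section 1 states that the SAP prevails over the protocol where they differ.

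**The concern.** IL-6 reduction is the stated rationale for the drug, and calprotectin sits under the SAP's heading for key or confirmatory secondary endpoints. These models will therefore be read as evidence on mechanism. Three features of the specification matter:

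- **Stratum.** A factor used to stratify randomization normally belongs in the analysis model. Leaving it out does not bias the comparison of arms balanced on it. If it is prognostic, though, its share of the variance stays in the error term and the standard errors come out too large.
- **Random effect.** A participant random intercept on top of an unstructured covariance cannot be separated from it. The SAP makes a convergence problem the trigger for simpler covariance structures, so a redundancy in the wording could end up choosing the covariance model.
- **Scale.** With no rule stated, change will be analysed on the raw scale, and SAP 5.3.2 keeps every reported value. If the markers are strongly right-skewed, power is lost. Choosing a log scale after seeing the data would be open to challenge.

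**Working it through.** **Plan's own figure.** The documents give no SD, effect size or power for IL-6, D-dimer or calprotectin, so there is nothing to reproduce.

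**1. Stratum: texts side by side**

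| Analysis | Remdesivir in the model? |
|---|---|
| Protocol 9.4.4, IL-6 and D-dimer | Yes |
| SAP 5.9.2, IL-6 and D-dimer | No |
| SAP 5.6.1, calprotectin | No (no protocol counterpart) |
| SAP 5.5.2, primary Cox and primary MMRM | Yes |
| SAP 5.6.2, discharge readiness (same approach as the primary Cox) and ordinal-scale CMH | Yes |
| SAP 5.7, ventilation CMH and viral load (same approach as the primary MMRM) | Yes |

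Only the three biomarkers lack it, no reason is given, and the SAP prevails.

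**2. Random effect: parameter count**

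With T post-baseline visits, J the all-ones matrix and R the within-participant matrix, the marginal covariance is V = σ_b²·J + R. If R is unstructured, replacing σ_b² by σ_b² + c and R by R − c·J leaves V unchanged, so the likelihood cannot separate the two. V has T(T+1)/2 distinct elements and the model has T(T+1)/2 + 1 covariance parameters:

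- T = 4 (Days 10, 14, 21, 28): 4×5/2 = 10 estimable, 11 specified.
- T = 5 (Day 5 added): 5×6/2 = 15 estimable, 16 specified.

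A numerical rank check of the derivative of V gave the same counts. For the fallbacks:

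- Compound symmetry plus the random intercept has 3 parameters at rank 2, so it is redundant too.
- Heterogeneous Toeplitz plus the random intercept is full rank when variances differ (8 of 8 at T = 4) and one short when they are equal (7 of 8).

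If the unstructured model fits, V and the treatment estimates are the same with or without the random effect.

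**3. Scale: illustration on assumed inputs**

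From the documents: 80 active and 40 control. Assumed: log-normal marker, correlation 0.6 between log baseline and log follow-up, geometric mean ratio 0.6, one visit, complete data. Each simulated trial was analysed twice by ANCOVA, as raw change on raw baseline and as log value on log baseline, two-sided 5%, with at least 3,000 trials per scenario.

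| Assumed log-SD | Power, raw | Power, log |
|---|---|---|
| 0.5 | about 100% | about 100% |
| 0.7 | 97% | 99% |
| 1.0 | 71% | 90% |
| 1.3 | 43% | 71% |

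Repeat runs agree to within about three percentage points.

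If instead the drug halves values only in participants above the median baseline, raw versus log power is 61% versus 58% at log-SD 1.0 and 40% versus 39% at 1.3. The log advantage is gone.

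Under no effect, two-sided type I error on the raw scale was 4.0% to 4.9% for log-SD 0.3 to 1.5. The tails become unequal. At log-SD 1.5 with correlation 0.5, the lower tail (apparent reduction on drug) rejects 3.0% and the upper 1.2%, against 2.5% each. SAP 5.1 reports one-sided p-values, so the tail favouring the drug is slightly liberal.

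**The case against.** The strongest reply is that these are secondary biomarker analyses without multiplicity control, that protocol 9.4 lets the SAP modify the protocol's plans, and that the SAP model is in other respects fuller than the protocol's: it names baseline, visit and their interaction with treatment, which protocol 9.4.4 does not. Descriptive medians and quartiles (SAP 5.1) would show skew. All of this is true. It limits the consequence but gives no reason for leaving out a stratification factor that the SAP keeps everywhere else.

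A reader might also infer more than the documents support:

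- **That the SAP introduced the random effect.** It did not. Protocol 9.4.4 already treats subjects as random with an unstructured covariance, so both texts need the edit.
- **That the stratum was dropped from the calprotectin model.** The protocol has no calprotectin endpoint, so there was no earlier model to drop it from.
- **That compound symmetry is forced.** AIC chooses between two fallback structures, and only if convergence fails. No failed fit has been shown, and the practical harm may be no more than a software warning.
- **That these markers are skewed and power is lost.** The documents give no distribution for them. The power gap rests on assumed log-SDs and one constant multiplicative effect. It nearly vanishes at log-SD 0.5 to 0.7 and disappears if only participants with high baseline values respond. The SAP's own subgroup by median baseline IL-6 (5.9.3) makes that last pattern worth taking seriously.

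**Conclusion.** The point holds as a specification defect of moderate consequence.

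- **Stratum.** SAP 5.9.2 omits a term that protocol 9.4.4 includes, and SAP 5.6.1 omits it for calprotectin. This follows from the texts alone. Its size cannot be stated, because the documents give no relation between remdesivir use and these markers.
- **Random effect.** It is redundant by exactly one parameter under the unstructured covariance, whatever the number of visits. Estimates do not change if the model fits. The risk is a fallback triggered for a technical reason.
- **Scale.** The documents establish only that no transformation rule exists here while one exists for viral load. The cost ranges from nothing at log-SD 0.5 to 28 percentage points of power at log-SD 1.3 (71 − 43), given the assumptions above. The simulation is a single-visit ANCOVA with complete data, not the planned repeated-measures model. Two-sided type I error is not inflated.

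**What to change.** 1. Add the remdesivir stratum as a fixed effect in SAP 5.6.1 and 5.9.2.
2. Delete the participant random effect in both sections and in protocol 9.4.4. Keep participant as the subject identifier for the unstructured covariance, as the primary MMRM effectively does.
3. Before database lock, pre-specify analysis of log IL-6, log D-dimer and log calprotectin with log baseline as covariate, reported as geometric mean ratios. At minimum, carry over the conditional log-transform rule that SAP 5.7 gives for viral load.

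Items 1 and 2 are wording changes with no statistical downside. The protocol edit can go into the amendment that SAP 5.10 says is planned. Item 3 means that results read as ratios rather than differences, and it would not gain power if the effect is confined to participants with high baseline values.
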